5. STUDY POPULATION

This study can fulfill its objectives only if appropriate participants are enrolled. The following eligibility criteria are designed to select participants for whom participation in the study is considered appropriate. All relevant medical and nonmedical conditions should be taken into consideration when deciding whether a particular participant is suitable for this protocol.

Prospective approval of protocol deviations to recruitment and enrollment criteria, also known as protocol waivers or exemptions, is not permitted.

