10. Other acute or chronic medical or psychiatric condition including recent (within the past year) or active suicidal ideation or behavior or laboratory abnormality that may increase the risk associated with study participation or investigational product administration or may interfere with the interpretation of study results and, in the judgment of the investigator, would make the participant inappropriate for entry into this study.

Prior/Concomitant Therapy:

11. Participation in other studies involving investigational drug(s) within 28 days prior to study entry and/or during study participation.
12. Participants who receive treatment with immunosuppressive therapy including cytotoxic agents or systemic corticosteroids (such as for cancer or an autoimmune disease), or planned receipt of such treatment or agents during study participation. If systemic corticosteroids have been administered short term (<14 days) for treatment of an acute illness, participants should not be enrolled into the study until corticosteroid therapy has been discontinued for at least 30 days before investigational product administration. Inhaled/nebulized, intra-articular, intrabursal, or topical (skin or eyes) corticosteroids are permitted.
13. Current alcohol abuse or illicit drug use.
14. Receipt of blood or plasma products or immunoglobulin, from 60 days before investigational product administration, or planned receipt through delivery, with 1 exception, Rho(D) immune globulin (eg, RhoGAM), which can be given at any time.

Prior/Concurrent Clinical Study Experience:

15. Previous vaccination with any licensed or investigational RSV vaccine or planned receipt during study participation.

Diagnostic Assessments:

16. Laboratory test results at the screening visit outside the normal reference value for pregnant women according to their trimester in pregnancy.

Note: With the exception of bilirubin, participants with any stable Grade 1 abnormalities (according to the toxicity grading scale²⁸) may be considered eligible at the discretion of the investigator. (Note: A “stable” Grade 1 laboratory abnormality is defined as a report of Grade 1 on an initial blood sample that remains ≤ Grade 1 upon repeat testing on a second sample from the same participant.)

Other Exclusions:

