8.10. Procedures

8.10.1. Maternal

8.10.1.1. Maternal Participants: Screening (Visit 0) Days -14 to -2 Prior to Vaccination

Maternal participants will be screened from 2 to 14 days prior to administration of the investigational product to confirm that they meet eligibility (all of the inclusion and none of the exclusion) criteria for the study. Maternal participants may be screened 1 day prior to administration of the investigational product if laboratory results are available prior to vaccination.

With the exception of bilirubin, if any Grade 1 hematology or blood chemistry abnormalities are found from samples taken at the screening visit and the investigator believes the results to be erroneous or to represent a stable Grade 1 abnormality, a retest of the abnormal laboratory parameters may be conducted. Maternal participants with stable Grade 1 abnormalities may be considered eligible at the discretion of the investigator.

A “stable” Grade 1 laboratory abnormality is defined as a report of Grade 1 on an initial blood sample that remains \leq Grade 1 upon repeat testing on a second sample from the same maternal participant.

If the maternal participant is found ineligible for the study based on a full assessment of inclusion and exclusion criteria, the investigator may advise the participant, either by

telephone or face to face, that the participant will be withdrawn from further participation in the study. All eligible maternal participants will proceed to the vaccination visit.

The following procedures will be performed:

- Obtain written informed consent before performing any study-specific procedures.
- Ensure and document that all of the inclusion criteria and none of the exclusion criteria are met.
- Assign a single participant identifier using the IRT system.
- Obtain and record the participant demography (including complete date of birth [dd-Mmm-YYYY], sex, race, and ethnicity). The date of birth will be collected to critically evaluate the immune response and safety profile by age.
- Obtain and record current alcohol, tobacco, and marijuana usage.
- Obtain and record any medical and obstetric history of clinical significance including history from prior and current pregnancy(ies). Refer to the SRM for further details.
- Record the last menstrual period (LMP) and estimated delivery date (EDD).
- Measure vital signs, including oral temperature, seated blood pressure, and heart rate.
- Measure and record weight and height.

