10.2.2. Hematology and Blood Chemistry

Blood samples for hematology and blood chemistry assessments (approximately 10 mL) will be collected for all maternal participants at screening (Visit 0).

Repeat testing of the protocol-required laboratory parameters is permitted to confirm results. Additional laboratory testing not specified in the protocol may be performed at the discretion of the investigator as follow-up to an AE and should be recorded in the maternal participant's source documents. The safety laboratory tests in Table 7 will be performed at times defined in the [SoA](#).

Table 7. Laboratory Tests

Hematology	Chemistry
Hemoglobin	BUN and creatinine
Hematocrit	AST, ALT
RBC count	Total bilirubin
Platelet count	Alkaline phosphatase
WBC count	
Total neutrophils (Abs)	
Eosinophils (Abs)	
Monocytes (Abs)	
Basophils (Abs)	
Lymphocytes (Abs)	

Abbreviations: Abs = absolute; ALT = alanine aminotransferase; AST = aspartate aminotransferase; BUN = blood urea nitrogen; RBC = red blood cell; WBC = white blood cell.

A toxicity grading scale adapted for use in pregnant women will be used to grade laboratory test abnormalities.²⁸

If abnormal laboratory parameters are reported at screening (Visit 0) and the investigator believes the results to be erroneous, the abnormal laboratory parameters may be retested.

10.3. Appendix 3: Adverse Events: Definitions and Procedures for Recording, Evaluating, Follow-up, and Reporting

For maternal immunization clinical studies conducted in pregnant women, data on the EDP as well as pregnancy outcome are collected and analyzed in the clinical database. For these studies, in general, EDP cases are not reportable unless associated with SAEs/nonserious AEs.

The term “participant” in this section refers to (1) the maternal participant and her fetus; and after delivery (2) the maternal participant and (3) the infant participant.

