3.5.4. Laboratory Data

Blood samples for hematology and blood chemistry assessments (approximately 10 mL) will be collected for all maternal participants at screening.

Assessments will include:

- Hematology: hemoglobin, hematocrit, red blood cell (RBC) count, platelet count, white blood cell (WBC) count, total neutrophils (absolute [Abs]), eosinophils (Abs), monocytes (Abs), basophils (Abs), and lymphocytes (Abs).
- Blood chemistries: alanine aminotransferase (ALT), aspartate aminotransferase (AST), alkaline phosphatase, total bilirubin, blood urea nitrogen (BUN), and creatinine.

The toxicity grading scale in [Table 7](#) below for pregnant women will be adapted, as appropriate (eg, based on the pregnancy status at the visit), for grading laboratory test abnormalities.

Table 7. Hematology and Blood Chemistry Toxicity Grading Scale

	Pregnancy Status	Normal Range	Mild (Grade 1)	Moderate (Grade 2)	Severe (Grade 3)	Grade 4
Female hemoglobin (Hb), g/dL	Second trimester	9.7-14.8	9.0-9.6	8.0-8.9	7.0-7.9 or requires a transfusion	<7.0 or life-threatening acute blood loss
	Change from baseline		1.6-2.0	2.1-4.5	4.6-5.0	>5.0
	Third trimester	9.5-15.0	9.0-9.4	8.0-8.9	7.0-7.9 or requires a transfusion	<7.0 or life-threatening acute blood loss
	Change from baseline		1.6-2.0	2.1-4.5	4.6-5.0	>5.0
Platelets high, 1000 cells/mm³	Second trimester	155-409	410-499	500-749	750-1000	>1000
	Third trimester	146-429	430-499	500-749	750-1000	>1000
Platelets low, 1000 cells/mm³	Second trimester	155-409	125-154	100-124	25-99	<25
	Third trimester	146-429	125-146	100-124	25-99	<25
WBCs^a high, 1000 cells/mm³	Second trimester	5.6-14.8	>14.8-16.0	>16.0-20.0	>20.0-25.0	>25.0 signs of septic shock
	Third trimester	5.9-16.9	>16.9-18.0	>18.0-20.0	>20.0-25.0	>25.0 signs of septic shock
WBCs^a low, 1000 cell/mm³	Second trimester	5.6-14.8	<5.5-3.5	<3.5-1.4	<1.4-1.0	<1.0 signs of septic shock
	Third trimester	5.9-16.9	<5.9-3.5	<3.5-1.4	<1.4-1.0	<1.0 signs of septic shock
Neutrophils (absolute neutrophil count), 1000 cells/mm³	Second trimester	3.8-12.3	<3.8-2.0	<2.0-1.0	<1.0-0.5	<0.5
	Third trimester	3.9-13.1	<3.9-2.0	<2.0-1.0	<1.0-0.5	<0.5
Eosinophils (absolute), 1000 cells/mm³	Second trimester	0-0.6	>0.6-1.5	>1.5-5.0	>5.0	Hypereosinophilic
	Third trimester	0-0.6	>0.6-1.5	>1.5-5.0	>5.0	Hypereosinophilic
Monocytes (absolute), 1000 cells/mm³	Second trimester	0.1-1.1	≤10% outside normal range	>10% outside range: clinical correlation may be necessary and grading according to it		

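### SAP Table 7 does not give every laboratory value exactly one grade; second-trimester alkaline phosphatase is the clearest case, and criterion 16 inherits the ambiguity if sites use that table.

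*Protocol*

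**What the plan says.** Protocol Section 5.2.1, criterion 16, excludes a woman for "Laboratory test results at the screening visit outside the normal reference value for pregnant women according to their trimester in pregnancy". The note beneath it gives one exception: "With the exception of bilirubin, participants with any stable Grade 1 abnormalities (according to the toxicity grading scale", cited as reference 28) may be admitted at the investigator's discretion. A stable abnormality "is defined as a report of Grade 1 on an initial blood sample that remains" no higher than Grade 1 on a second sample. Section 5 adds that prospective approval of deviations from the entry criteria, "also known as protocol waivers or exemptions, is not permitted".

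On the scale itself, Protocol Section 10.2.2 says "A toxicity grading scale adapted for use in pregnant women will be used to grade laboratory test abnormalities", again citing reference 28. The protocol does not print the scale. SAP Section 3.5.4 prints one as Table 7 and says that the scale "below for pregnant women will be adapted, as appropriate (eg, based on the pregnancy status at the visit), for grading laboratory test abnormalities". SAP Section 6.6.3 plans descriptive summaries of screening laboratory abnormalities by vaccine group, with listings of women who have abnormal results.

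**The concern.** A grading scale has to send each value to one grade. Table 7 fails this in several cells. In the second-trimester alkaline phosphatase row, one range has two grades and another, just above normal, has none.

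Two uses are at stake. The first is certain: Table 7 is the SAP's own rule for grading laboratory abnormalities, so a programmer would have to choose a grade for these values when producing the screening summaries. The second is conditional. Under criterion 16, whether an out-of-range value is Grade 1 or Grade 2 decides whether the woman may be admitted. If sites grade on Table 7, two sites could treat the same result differently. Membership of the evaluable maternal population also requires eligibility (SAP Section 4), so the ambiguity could then reach the secondary immunogenicity analyses.

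**Working it through.** No sample-size or power figure is involved. The check applies the printed bands to the printed normal limits.

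**Second-trimester alkaline phosphatase.** Inputs from SAP Table 7: normal 25-126 U/L, so ULN = 126; Grade 1 is 1.1-2.0 x ULN; Grade 2 is >1.2-3.0 x ULN.

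- Grade 1: 1.1 x 126 = 138.6 to 2.0 x 126 = 252
- Grade 2: above 1.2 x 126 = 151.2, to 3.0 x 126 = 378

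| Value (U/L) | Printed grade |
|---|---|
| 25 to 126 | normal |
| >126 to <138.6 | none |
| 138.6 to 151.2 | 1 |
| >151.2 to 252 | 1 and 2 |
| >252 to 378 | 2 |

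The overlap takes up (252 - 151.2) / (252 - 138.6) = 100.8 / 113.4 = 89% of the Grade 1 band, so it is more than a boundary effect.

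**Third-trimester row, for comparison.** ULN = 229; Grade 1 is >1.0-1.2 x ULN, which is >229 to 274.8; Grade 2 is >1.2-3.0 x ULN, which is >274.8 to 687. There is no overlap, and no gap above the ULN.

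**Smaller slips in the same table.**

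- White cells, second trimester: normal starts at 5.6, and Grade 1 is printed as <5.5-3.5. A result of 5.5 is below normal and ungraded.
- Platelets, third trimester: normal is 146-429 and low Grade 1 is 125-146. A result of 146 is both.
- ALT, second trimester (ULN 33): Grade 3 ends at 8.0 x 33 = 264, and Grade 4 starts above 10 x 33 = 330. Values >264 to 330 are ungraded.
- Bilirubin with normal liver tests, third trimester (ULN 1.1): Grade 1 ends at 1.5 x 1.1 = 1.65, and Grade 2 starts above 1.6 x 1.1 = 1.76. Values >1.65 to 1.76 are ungraded.

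**What this would do under criterion 16, if Table 7 is the cited scale.** Stable second-trimester alkaline phosphatase results:

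- 130 U/L (130/126 = 1.03 x ULN): out of range with no grade, so not spared and excluded.
- 145 U/L (1.15 x ULN): Grade 1 only, so may be admitted.
- 160 U/L (1.27 x ULN): may be admitted on the Grade 1 column, excluded on the Grade 2 column.

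The row also runs backwards: the value nearest to normal is the one certainly excluded.

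**Out-of-range directions with no grade.** Of the 16 screening analytes, hematocrit and RBC count have no row. Leaving bilirubin aside, seven directions have a normal limit but no grade beyond it: high hemoglobin, high neutrophils, and low BUN, creatinine, AST, ALT and alkaline phosphatase.

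**The case against.** The strongest objection is that criterion 16 does not invoke Table 7. It cites reference 28, which Protocol Section 10.2.2 and the vaccination-visit procedures cite too. Table 7 sits in an analysis document and is itself to be adapted as appropriate. This stands: the eligibility consequence is conditional. It does not remove the grading problem, because SAP Section 3.5.4 makes Table 7 the SAP's own scale.

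The consequence is also limited. Scheduled laboratory tests are done only at screening and feed descriptive output, not a primary or secondary endpoint. Admission of a Grade 1 result is discretionary anyway. That limits the weight of the point but does not justify leaving two grades on one value.

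Four stronger readings are tempting, and the documents do not support them.

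- A reader might infer that every ungraded value makes a woman both eligible and excluded. It does not. An ungraded out-of-range value fails the Grade 1 exception and therefore excludes. That is strict and asymmetric (a high BUN can be spared, a low one cannot), but it is not a contradiction.
- A reader might infer that all the slips change eligibility. Platelets of 146 are within the printed normal range, the ALT gap lies far above Grade 1, and bilirubin is never spared. Only the alkaline phosphatase row and the single white-cell value of 5.5 could matter.
- A reader might see a conflict over retesting. Section 8.10.1.1 deals with the case "With the exception of bilirubin, if any Grade 1 hematology or blood chemistry abnormalities are found from samples taken at the screening visit" and permits a retest; Section 10.2.2 says that where "the investigator believes the results to be erroneous, the abnormal laboratory parameters may be retested". The first is permissive and does not bar the second, so both can be followed.
- A reader might want the share of healthy women screened out. The documents give no distribution for any analyte, so no credible percentage can be offered.

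**Conclusion.** The point holds as a defect in SAP Table 7. In the second trimester, alkaline phosphatase of >151.2 to 252 U/L carries two grades and >126 to <138.6 U/L carries none, and four other cells have smaller gaps or overlaps. The clean third-trimester alkaline phosphatase row suggests a drafting slip rather than an intended rule.

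The effect on the screening laboratory output follows from the SAP alone, although the ALT and bilirubin values should seldom appear there because such women are excluded. The effect on eligibility rests on one assumption that the documents neither state nor rule out: that Table 7 is the reference 28 scale sites use. It would then concern women graded on the second-trimester rows; entry from 24 0/7 weeks makes those rows relevant. The number affected is unknown. The correction is worth making because it is specific and cheap, and because waivers are not available to repair a misread criterion.

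**What to change.** Three changes, with the clinical content left to the sponsor:

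1. Reconcile SAP Table 7 so that each value falls in exactly one category: second-trimester alkaline phosphatase, second-trimester low white cells, third-trimester low platelets, second-trimester ALT, and third-trimester bilirubin with normal liver tests. Which limits are right is for the sponsor to decide.
2. Confirm in the protocol or SAP whether Table 7 is the reference 28 scale used for criterion 16. If it is not, explain any difference between the two.
3. State how an out-of-range result with no grade (for example hematocrit, RBC count, high hemoglobin or low BUN) is handled under criterion 16 and in the laboratory summaries.

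The cost is one corrected table and a few sentences. No new test, visit or data item is needed.

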5.2.2. Exclusion Criteria – Infant Participants

1. Infant who is a direct descendant (eg, child or grandchild) of the study personnel.

5.2.3. Temporary Vaccination Delay Criteria – Maternal Participants

The following conditions are temporary or self-limiting and a maternal participant may be vaccinated once the condition(s) has/have resolved and if no other exclusion criteria are met. The prevaccination blood draw and vaccination should take place on the same day.

5.2.3.1. Criteria for Temporarily Delaying Vaccine Administration – Maternal Participants

- Current febrile illness (body temperature $\geq 100.4^{\circ}\text{F}$ [$\geq 38^{\circ}\text{C}$]) or other acute illness within 48 hours before investigational product administration.
- Receipt of any inactivated vaccine within 14 days or any live vaccine within 28 days before investigational product administration.
- Receipt of short-term (<14 days) systemic corticosteroids. Investigational product administration should be delayed until systemic corticosteroid use has been discontinued for at least 30 days. Inhaled/nebulized, intra-articular, intrabursal, or topical (skin or eyes) corticosteroids are permitted.

5.3. Lifestyle Considerations

No restrictions are required.

5.4. Screen Failures

Screen failures are defined as participants who consent to participate in the clinical study but are not subsequently randomly assigned to investigational product. A minimal set of screen failure information is required to ensure transparent reporting of screen failure participants to meet the Consolidated Standards of Reporting Trials (CONSORT) publishing requirements and to respond to queries from regulatory authorities. Minimal information includes demography, screen failure details, eligibility criteria, and any SAE.

Individuals who do not meet the criteria for participation in this study (screen failure) may be rescreened.

6. STUDY INTERVENTION

Study intervention is defined as any investigational intervention(s), marketed product(s), placebo, or medical device(s) intended to be administered to a study participant according to the study protocol.

For the purposes of this protocol, the term investigational product may be used synonymously with study intervention.

6.1. Study Intervention(s) Administered

For this study, the investigational product(s) are RSV vaccine and placebo (saline control).

6.1.1. Respiratory Syncytial Virus Stabilized Prefusion F Subunit Vaccine

Each lyophilized vial of the RSV vaccine drug product will be supplied as a mixture of equal quantities of 2 stabilized prefusion RSV F antigens, 1 from each of the RSV subgroups A and B in a lyophilized cake.

The lyophilized drug product contains excipients which, after reconstitution, will yield a solution as detailed in Table 1 below.

There are 2 different presentations of RSV drug product representing 2 different dose levels of RSV antigen (120 µg and 240 µg). The lyophilized cake is reconstituted by diluent with either sterile water for injection or a sterile suspension of Al(OH)₃ in water for injection. The stopper of the sterile water for injection vial may contain natural rubber latex.

The fill volume of the drug product vial and diluent vial are designed such that the intended vaccine dose is delivered in a 0.5-mL injection volume. CCI

CCI

6.1.2. Placebo

The placebo will be a sterile normal saline solution for injection (0.9% sodium chloride injection, in a 0.5-mL dose).

Placebo will be provided by the sponsor to each study site. Placebo will be packaged within cartons labeled by Pfizer or its designee in accordance with current guidelines and applicable local and legal regulatory requirements.

6.1.3. Administration

Maternal participants will receive 1 dose of investigational product at the vaccination visit in accordance with the study's SoA. The investigational product will be administered intramuscularly by injecting 0.5 mL into the deltoid muscle of the nondominant arm by the appropriately designated study staff at the investigator site.

Standard vaccination practices must be observed and vaccine must not be injected into blood vessels. Appropriate medication and other supportive measures for management of an acute hypersensitivity reaction should be available in accordance with local guidelines for standard immunization practices.

Administration of investigational products should be performed by an appropriately qualified, Good Clinical Practice (GCP)-trained, and vaccine-experienced member of the study staff (eg, physician, nurse, physician's assistant, nurse practitioner, pharmacist, or medical assistant) as allowed by local, state, and institutional guidance.

Investigational product administration details will be recorded on the case report form (CRF).

6.2. Preparation/Handling/Storage/Accountability

- The investigator or designee must confirm appropriate temperature conditions have been maintained during transit for all study interventions received and any discrepancies are reported and resolved before use of the study intervention, as applicable for temperature-monitored shipments.
- Only maternal participants enrolled in the study may receive study intervention and only authorized site staff may supply or administer study intervention. All study interventions must be stored in a secure, environmentally controlled, and monitored (manual or automated recording) area in accordance with the labeled storage conditions with access limited to the investigator and authorized site staff. At a minimum, daily minimum and maximum temperatures for all site storage locations must be documented and available upon request. Data for nonworking days must indicate the minimum and maximum temperature since previously documented for all site storage locations upon return to business.
- The investigator, institution, or the head of the medical institution (where applicable) is responsible for study intervention accountability, reconciliation, and record maintenance (ie, receipt, reconciliation, and final disposition records). All study interventions will be accounted for using an investigational product accountability form/record.
- Further guidance and information for the final disposition of unused study interventions are provided in the investigational product manual (IP manual).
- Any storage conditions stated in the SRSD will be superseded by the storage conditions stated on the product label.

- Study interventions should be stored in their original containers and in accordance with the labels.
- See the IP manual for storage conditions of the study intervention once reconstituted.
- Any excursions from the study intervention label storage conditions should be reported to Pfizer upon discovery along with any actions taken. The site should actively pursue options for returning the study intervention to the storage conditions described in the labeling, as soon as possible. Once an excursion is identified, the study intervention must be quarantined and not used until Pfizer provides permission to use the study intervention. It will not be considered a protocol deviation if Pfizer approves the use of the study intervention after the temperature excursion. Use of the study intervention prior to Pfizer approval will be considered a protocol deviation. Specific details regarding the definition of an excursion and information the site should report for each excursion will be provided to the site in the IP manual.
- The sponsor or designee will provide guidance on the destruction of unused study intervention (eg, at the site). If destruction is authorized to take place at the investigator site, the investigator must ensure that the materials are destroyed in compliance with applicable environmental regulations, institutional policy, and any special instructions provided by Pfizer, and all destruction must be adequately documented.

Additional details about accountability, storage, destruction, and excursion reporting can be found in the IP manual.

